#### **Missing/Partial Dates of Initial Diagnosis**

Dates of initial diagnosis that are partially missing will be imputed as follows:

- If month and year are present but day is missing, 15 will be used to impute the missing day.
- If only year is present but day and month are missing, the 01JUL will be used to impute the missing day and month.

Statistical Analysis Plan Version Number: 1.0

If this imputation rule yields a date of initial diagnosis after enrollment date, then the partial date of the initial diagnosis will be imputed as 01JAN when only year is provided and the first day of the month when only month and year are provided.

## 4.3 Study Endpoints

All PK related analyses of endpoints described below will done independently under a separate PK analysis plan and such analyses are not covered under this analysis plan.

#### 4.3.1 Dose Escalation

#### Primary:

• Dose-limiting toxicity, MTD, and RP2D.

#### Secondary:

- PK parameters of PEGPH20: maximum observed concentration ( $C_{max}$ ), minimum observed concentration ( $C_{min}$ ), terminal elimination half-life ( $T_{1/2}$ ), area-under-the-concentration time curve (AUC), volume of distribution ( $V_D$ ) and clearance (CL).
- ORR, DOR, DCR, and PFS based on RECIST v1.1.
- OS.

#### Exploratory:

• PK parameters of pembrolizumab:  $C_{max}$ ,  $C_{min}$ ,  $T_{1/2}$ , AUC,  $V_D$  and CL.

#### 4.3.2 Dose Expansion

#### **Primary**:

• ORR based on RECIST v1.1.

#### Secondary:

- DOR, DCR and PFS based on RECIST v1.1, and OS.
- ORR, DOR, DCR, and PFS based on irRC.
- PK parameters of PEGPH20:  $C_{max}$ ,  $C_{min}$ ,  $T_{1/2}$ , AUC,  $V_D$  and CL.
- Incidence of AEs.
- Changes in clinical safety laboratory values.
- Changes in cardiovascular parameters (electrocardiogram [ECG]) and vital signs.

#### Exploratory:

- ORR, DOR, DCR, and PFS based on RECIST v1.1 criteria and irRC by PD-L1 expression levels.
- Changes from pre-treatment in plasma HA and tumor HA (when available).
- Correlation between plasma HA levels pre-dose, post-dose and any pharmacodynamic response.

- Changes in tumor blood flow as measured by DCE-MRI.
- Changes in tumor metabolism as measured by PET/CT.
- Correlation of biomarkers in plasma and tumor biopsy to study endpoints.
- PK parameters of pembrolizumab:  $C_{max}$ ,  $C_{min}$ ,  $T_{1/2}$ , AUC,  $V_D$  and CL.

## 4.4 Analysis Populations

#### 4.4.1 Enrolled Population

The Enrolled Population is defined as all subjects who were enrolled (i.e., subjects who sign the informed consent form at the screening and are enrolled in a cohort) in the study. Subjects will be analyzed according to the initial cohort actually assigned.

#### 4.4.2 Safety Population

The Safety Population analysis set is defined as all enrolled subjects in either Dose Escalation or Dose Expansion portion of the study, who receive at least 1 dose of any study medication (PEGPH20 or pembrolizumab). The Safety Population will be used for drug exposure, demographics and safety analyses, including AE, labs, and deaths. Subjects will be analyzed according to the initial cohort actually assigned.

#### 4.4.3 DLT Evaluable Population

The DLT Evaluable Population is defined as all subjects enrolled in the Dose Escalation portion who receive at least 1 of the 3 full planned doses of PEGPH20 and 1 complete dose of pembrolizumab in Cycle 1 and have been followed for the first 21 days of treatment or have experienced a DLT during the initial 21 days (Cycle 1) of the study. DLTs will be assessed for each subject during the 21 days of Cycle 1 following their first PEGPH20 dose. The DLT Evaluable Population will be used for DLT analysis.

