To be considered evaluable for DLT assessment, subjects must receive 1 of the 3 full planned doses of PEGPH20 and 1 complete dose of pembrolizumab in Cycle 1. Subjects who experience a DLT within the first 21 days of treatment and withdraw from the study will be considered evaluable for DLT and will not be replaced. Subjects who withdraw within the first 21 days for reasons other than a DLT will be considered not evaluable and will be replaced. Any PEGPH20 treatment-related AE that results in interruption or reduction of either drug (PEGPH20 or pembrolizumab) may be considered a DLT at the Investigator's discretion.

The Sponsor and the participating Investigators will meet as soon as practical, post completion of a cohort, and no more than 10 business days after the end of the last cohort to determine an acceptable dose for the Dose Expansion portion after reviewing all available safety data from Cycle 1 from all subjects in the Dose Escalation portion.

Table 4: Dose Allocation and Cohort Schedule - Dose Escalation Portion

Dose Level	PEGPH20 μg/kg	Pembrolizumab mg/kg
-1	1.0	2
1	1.6	2
2	2.2	2
3	2.6	2
4	3.0	2
5	4.0^{a}	2

Abbreviations: PEGPH20 = PEGylated Recombinant Human Hyaluronidase.

Note: Each treatment cycle is 21 days. Dose interruption and modifications are permitted.

^a If the MTD is not reached at 4.0 μg/kg, higher doses may be evaluated.

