11.1.3.2. DLT Evaluable Population

All subjects who receive at least 1 of the 3 full planned doses of PEGPH20 and 1 complete dose of pembrolizumab in Cycle 1 and have been followed for the first 21 days of treatment or have experienced a DLT during the initial 21 days (Cycle 1) of the study. The DLT Evaluable Population will be used for DLT analysis.

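### The DLT-evaluability rules conflict, and a subject whose DLT prevents a complete pembrolizumab dose but who stays in follow-up can be left out of the DLT analysis

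*SAP*

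**What the plan says.** Three places govern who counts as DLT-evaluable.

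- **Protocol 6.1.1 (repeated in the Synopsis).** To be evaluable, "subjects must receive 1 of the 3 full planned doses of PEGPH20 and 1 complete dose of pembrolizumab in Cycle 1". That sentence makes no exception for a DLT. The next sentence covers subjects who have a DLT in the first 21 days and also leave the study: they "withdraw from the study will be considered evaluable for DLT and will not be replaced". Replacement is then confined to others: "Subjects who withdraw within the first 21 days for reasons other than a DLT will be considered not evaluable and will be replaced".
- **Protocol 11.1.3.2.** After the same dosing minimum, the definition requires that subjects "have been followed for the first 21 days of treatment or have experienced a DLT during the initial 21 days (Cycle 1" (the parenthesis closes after the quoted words).
- **SAP 4.4.3.** The set consists of Dose Escalation subjects "who receive at least 1 of the 3 full planned doses of PEGPH20 and 1 complete dose of pembrolizumab in Cycle 1" who were also followed for 21 days or "have experienced a DLT during the initial 21 days (Cycle 1) of the study".

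SAP 4.9.3 tabulates DLTs on this population only. SAP 4.3.1 lists DLT, MTD and RP2D as the primary endpoints of Dose Escalation. Protocol 6.1.1 and SAP 3.1.1 define the MTD by a count of evaluable subjects (at most 1 of 6 with a DLT).

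**The concern.** A toxicity severe enough to be dose-limiting may also be the reason the second drug is not given or not finished. Pembrolizumab follows PEGPH20 by 4-6 hours on Day 1 (Protocol 8.3.2.1), so a related Grade 3 or higher event in that interval could lead to its being withheld. Protocol 6.1.1 also lets the Investigator call a PEGPH20-related event a DLT when it interrupts either drug. If the first pembrolizumab infusion is interrupted for that reason and never completed, one event both creates the DLT and defeats the dosing minimum.

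If evaluability depends on completing pembrolizumab, such a subject is removed because of the outcome being measured. The exclusion acts in one direction: it can take DLTs out of the primary analysis but cannot add any.

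**Working it through.** No figure is stated for the DLT Evaluable Population. The nearest stated figure, about 30 Dose Escalation subjects, reproduces as 5 dose levels x 6 subjects = 30 and does not depend on this point. The check is therefore one of wording.

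**Step 1: the two readings of SAP 4.4.3 and Protocol 11.1.3.2.** Let A = dosing minimum met, B = followed for 21 days, C = DLT within 21 days.

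- Restrictive: A and (B or C).
- Inclusive: (A and B) or C.

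Grammatically, being followed and having experienced a DLT are parallel verb phrases placed after the dosing condition, which favours the restrictive reading. The dosing sentence in Protocol 6.1.1 points the same way; the DLT-withdrawal sentence after it points the other way.

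**Step 2: apply each rule to the possible subjects.**

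| Subject | 6.1.1 dosing sentence | 6.1.1 DLT-withdrawal sentence | Restrictive | Inclusive |
|---|---|---|---|---|
| DLT, dosing minimum met | not excluded | in, if withdrawn | in | in |
| DLT, no complete pembrolizumab, withdraws from study | out | in, not replaced | out | in |
| DLT, no complete pembrolizumab, stops treatment, stays in follow-up | out | silent | out | in |
| No DLT, dosing minimum not met | out | does not apply | out | out |

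The readings differ only in rows 2 and 3. In row 2, Protocol 6.1.1 contains its own exception, which the restrictive reading of the SAP would contradict. In row 3 there is no exception to appeal to. Row 3 is a realistic case: Protocol 7.3.1 and 7.3.2 separate stopping treatment from leaving the study, and subjects who stop both drugs go on to long-term follow-up.

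**Step 3: what one row-3 subject does to a count.** Take six dosed subjects with two DLTs, one of them in row 3.

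- Inclusive: 2/6 = 33%.
- Restrictive, nobody replaced: (2 - 1)/(6 - 1) = 1/5 = 20%.

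This shows direction only; the documents do not say how often row 3 would occur.

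**Step 4: how wide the opening is.** On schedule, the event must arise between the two drugs or during the 30-minute pembrolizumab infusion. Protocol 6.1.1 excludes hypersensitivity and infusion reactions from the DLT definition, and counts a Grade 3 musculoskeletal event only if it fails to improve to Grade 2 or lower within 48 hours. A held first pembrolizumab dose would widen the interval. The expected number of affected subjects is small.

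**The case against.** The strongest reply is that this is a missing bracket. The inclusive reading is possible and keeps every DLT. Protocol 6.1.1 supports it by stating "Subjects who experience a DLT within the first 21 days of treatment and withdraw from the study will be considered evaluable for DLT", and SAP 4.9.1 sends the reader to that same section for the DLT definition. The rule that two or more DLTs stop escalation refers to subjects at a dose level, without the word evaluable. The RP2D draws on safety data from all dosed subjects. Related Grade 3 or higher events are tabulated in the Safety Population (SAP 4.9.4), so the toxicity would not vanish from the report. The SAP is dated 19 April 2019, after Dose Expansion enrollment stopped on 31 May 2018 (SAP 4.7.2), so its wording could not have steered escalation.

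All of this stands, and it limits the consequence. It does not settle row 3: the supporting sentence is conditional on withdrawal from the study, and the MTD sentence does use the evaluable count.

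A reader might go further and infer that early-DLT subjects are dropped and replaced, so that a toxic dose passes the 3+3 rule more often. With DLT rate p among evaluable subjects, the pass probability is (1-p)^3 + 3p(1-p)^5. If a share f of DLT subjects were dropped and replaced, p would become p(1-f)/(1-pf). At an assumed p = 0.33 the pass probability is 0.434, rising to 0.457, 0.480 and 0.558 for assumed f of 5%, 10% and 25%. The documents do not support this inference. They give neither p nor f, they say DLT withdrawals are not replaced, and they order no replacement in row 3.

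**Conclusion.** The point holds as a conflict between stated rules on a primary endpoint. On the more natural reading of SAP 4.4.3 and Protocol 11.1.3.2, a subject whose DLT prevents a complete pembrolizumab dose in Cycle 1 and who stays in follow-up falls outside the DLT table and the evaluable MTD count. Any resulting error understates toxicity. Two programmers could reasonably build different populations from the same text.

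The size cannot be derived from the documents. It depends on how many such subjects exist, which is likely to be few and may be none. Since escalation was over when the SAP was written, what is at stake in SAP 4.4.3 is the reported DLT and MTD analysis, not later dosing decisions.

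**What to change.** In SAP 4.4.3, define the population as: (dosing minimum met and followed for 21 days) or any DLT within 21 days of the first PEGPH20 dose, whatever doses were received. The dosing minimum then applies only to subjects without a DLT. Protocol 6.1.1 (with the Synopsis) and 11.1.3.2 should be reconciled to the same statement. If the protocol is no longer being amended, record the clarification in SAP Section 5. In the DLT listing already planned in SAP 4.9.3, flag any subject with a DLT who did not meet the dosing minimum, so that the effect of the definition is visible.

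The cost is one sentence in the SAP, the matching protocol text or a Section 5 entry, and a flag in a listing. Sample size is unchanged. The only downside is that the reported DLT count may be slightly higher.

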#### 4.4.4 PK Analysis Population

This analysis plan does not cover PK analysis. As appropriate, a description of PK analysis will be provided in a separate PK analysis plan.

#### 4.4.5 Efficacy Evaluable Population

All HA-high subjects who receive at least 1 dose of the RP2D of PEGPH20 and at least 1 dose of pembrolizumab in the Dose Expansion portion and all subjects who receive at least 1 dose of PEGPH20 and at least 1 dose of pembrolizumab in the Dose Escalation portion. The Efficacy Evaluable Population will be used for all efficacy analyses, except for tumor response related analyses.

#### 4.4.6 Tumor Response Evaluable Population

Subjects in the Efficacy Evaluable Population who have at least one post-baseline tumor assessment on or post Cycle 2. Tumor Response Evaluable Population will be used for all tumor response related analyses.

## 4.5 Subject Enrollment and Disposition

For subjects who discontinued from study treatment phase and discontinued from study, the primary reason for discontinuation will be summarized for all enrolled subjects by cancer type and in total. Further, the number of subjects included in each analysis population will be tabulated.

Major protocol deviations are defined as those deviations from the study protocol that are likely to have an impact on the subject's rights, safety, well-being, and/or on the validity of the data for analysis. Examples of possible major protocol deviations include, but are not limited to:

- a. Violation of eligibility criteria
- b. Dosing error of study drugs
- c. Excluded concomitant medication
- d. Subject withdrawal
- e. Study visits and procedures

The number and percentage of subjects with major protocol deviations by type of deviation will be summarized by cancer type and in total.

## 4.6 Demographics and Other Baseline Data

Demographics and other baseline data will be summarized by cancer type and using the Safety Population and by cancer type using the Efficacy Evaluable Population.

#### 4.6.1 Demographics

Age at Screening (years), height at Screening (cm), weight at Screening (kg), and body surface area (BSA; m^2) at Screening will be summarized descriptively (N, mean, standard deviation [SD], median, minimum [min], maximum [max], and quartiles). Age category at Screening (< 65 versus  $\geq$  65 years), sex, race, and ethnicity will be summarized by frequency counts and percentages.

Age at Screening will be calculated as follows:

```
Age at Screening = Integer \leq [(Date of Screening–Date of birth + 1) / 365.25].
```

BSA at Screening will be calculated using DuBois formula as follows:

BSA at Screening =  $0.007184 * W^{0.425} * H^{0.725}$ 

#### 4.6.2 Baseline Disease Characteristics

A descriptive summary of baseline disease characteristics of the subjects in the Safety Population and Efficacy Population by cancer type and in total will be produced for the following: initial disease stage, time from initial diagnosis to enrollment, current disease stage (months), time from current diagnosis to enrollment (months), significant past medical history or ongoing (yes, no), tobacco usage status (current, former, or never), alcohol usage status (current, former, or never), number of cancer therapy lines, prior cancer therapies/medications (yes, no), prior cancer resections (yes, no), prior cancer radiation (yes, no), PD-L1 expression level in tumor tissues on tumor cells assessed by NeoGenomics for subjects with gastric adenocarcinoma cancer type and Ventana for subjects with NSCLC cancer type at Baseline along with positive and negative status, and ECOG performance status at Screening and on study day 1.

The positive and negative status for PD-L1 on tumor cells at Baseline are determined based on the following (see prescribing information of Keytruda®):

- Subjects with gastric adenocarcinoma cancer type: the PD-L1 status is provided by NeoGenomics based on Combined Positive Score (CPS) where PD-L1 status is assigned as negative if CPS = 0 and positive if CPS ≥ 1.
- Subjects with NSCLC cancer type: the PD-L1 status will be derived based on Tumor Proportion Score (TPS) from Ventana data as follows:
  - If pembrolizumab is the first-line treatment, the PD-L1 status will be considered as negative if TPS < 50 and positive if TPS  $\ge$  50.
  - If pembrolizumab is the second-line treatment or beyond, the PD-L1 status will be considered as negative if TPS = 0 and positive if  $TPS \ge 1$ .

A listing of baseline disease characteristics will also be provided.

#### 4.6.3 Medical History and Prior Cancer Treatments

Medical/surgical history and prior cancer surgeries will be coded using the Medical Dictionary of Regulatory Activities (MedDRA) and will be listed for all subjects in the Enrolled Population.

Prior cancer treatments (medication) will be coded using the World Health Organization (WHO) Drug dictionary (WHO Drug) and will be summarized by preferred term for the Safety Population by cancer type and in total and also be listed for all subjects in the Enrolled Population.

#### 4.6.4 Prior and Concomitant Medications

Prior medications are those the subject used prior to the first dose date. Prior medications can be discontinued before first dosing or can be ongoing during treatment phase.

Concomitant medications are defined as medications that were either initiated prior to the first dose of study drug and continued during the study treatment, or initiated on or after the date of the first dose of study drug till the end of the last dose of study drug plus 30 days. A given medication can be classified both as a prior medication and as a concomitant medication depending on the start and stop dates.

A summary showing the number and percentage of subjects who took either prior and/or concomitant medications will be coded by WHO therapeutic drug class, and summarized separately by anatomic therapeutic class (ATC) and preferred term using frequencies and percentages for subjects in the Safety Population by cancer type and in total. In these summaries, subjects taking more than one medication in the same ATC or preferred name will be counted only once under that ATC or preferred term. All prior and concomitant medications will also be listed.

## 4.7 Efficacy Evaluations

All efficacy endpoints regarding response (i.e., ORR, DCR, and DOR) will be analyzed by cancer type [i.e., gastric adenocarcinoma and non-small cell lung cancer (NSCLC)] using the Tumor Response Evaluable Population for subjects for the Dose Escalation portion, Dose Expansion portion, and all subjects in both portions. The median DOR with two-sided 80% confidence intervals will be estimated using the Kaplan-Meier survival analysis methods. In addition, Kaplan-Meier estimates of rate of subjects with continuing response and the corresponding two-sided 80% confidence interval will also be provided.

All other efficacy endpoints (i.e., PFS and OS) will be analyzed by cancer type using the Efficacy Evaluable Population for the Dose Escalation portion, Dose Expansion portion, and all subjects in both portions. The median PFS, the median OS and two-sided 80% confidence intervals will be estimated using the Kaplan-Meier survival analysis methods. The Kaplan-Meier estimates of percent event-free for PFS, percent alive for OS and the corresponding two-sided 80% confidence intervals will also be provided.

All efficacy endpoints will be provided in listings for both Dose Escalation and Dose Expansion portions.

#### 4.7.1 Definitions

#### **Objective Response Rate**

Objective Response Rate (ORR) is defined as the proportion of subjects who achieve an objective response, which will be calculated as the number of subjects with a CR or PR divided by the number of subjects in the analysis population of interest (i.e., Tumor Response Evaluable Population) multiplied by 100. ORR is defined using the RECIST v1.1 and irRC by cancer type for the Dose Escalation portion, Dose Expansion portion, and all subjects in both portions.

The primary efficacy endpoint of the study in the Dose Expansion portion is PEGPEM treatment effect on ORR. A confirmed response requires a confirmatory scan showing a CR or PR at least 28 days apart from the initial observation of CR or PR. Any scans done within 28 days that show CR, PR or NE (not evaluable) cannot be used as a confirmatory scan. In addition, ORR without confirmed response (unconfirmed) will also be analyzed.

The best overall response categories (CR, PR, SD, PD, and NE) defined using the RECIST v1.1 and irRC will be analyzed in summary tables. Listings of these response categories will be provided for both Dose Escalation and Dose Expansion portions.

#### **Disease Control Rate**

Disease Control Rate (DCR) is defined as the proportion of subjects who achieve a best overall response of CR, PR, or Stable Disease (SD) and will be calculated as the number of subjects with a best overall response of CR, PR or SD divided by the number of subjects in the analysis population multiplied by 100. DCR defined using the RECIST v1.1 and irRC will be analyzed with both summary tables and listings.

#### **Duration of Response**

Duration of Response (DOR) is defined as the time from the date on which an objective response (CR or PR) is first determined until the first date on which radiographic disease progression is

Statistical Analysis Plan Version Number: 1.0

determined, and will only be calculated for subjects with an objective response (both confirmed and unconfirmed) for the Dose Escalation portion, Dose Expansion portion, and all subjects in both portions. Subjects achieving an objective response who do not have radiographic disease progression will be censored at the date of the last available post-baseline evaluable tumor assessment. DOR defined using the RECIST v1.1 and irRC will be analyzed with both summary tables and listings.

#### Progression-free Survival per RECIST v1.1

Progression-free survival (PFS), defined as the time from the first dose date until the first occurrence of either radiographic or clinical disease progression or death from any cause during the treatment period. Subjects without PFS event by the analysis cut-off date will have their PFS censored at the last evaluable post-baseline tumor assessment day or on Day 1 if they have no post-baseline tumor assessments. PFS (in months) will be calculated as:

```
(Event date or censoring date – First dose date + 1) / 30.4375
```

Because the dosing interval between cycles without a dose is 7 days (from Day 15 to Day 21 of each cycle), the treatment period will include 7 days after the last dose date. Thus, subjects who are not radiologically or clinically progressed, but died within 7 days of the last dose will be considered as having PFS events. Deaths after 7 days of last dose without radiological or documented clinical progression will not be considered as PFS events in the primary PFS analysis. Table 3 below describes the scheme of events and censoring for PFS.

